## **5.5 Participant Replacement Strategy**

If a participant discontinues from study intervention or withdraws from the study, a replacement participant may be enrolled if deemed appropriate by the investigator and Sponsor. The replacement participant will generally receive the same intervention or intervention sequence (as appropriate) as the participant being replaced. The replacement participant will be assigned a unique treatment/randomization number. The study site should contact the Sponsor for the replacement participant's treatment/randomization number.

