#### **4.2.2 Rationale for the Use of Comparator/Placebo**

A matched placebo-control will be included to reduce bias with regards to the participant reporting and investigator assessment of AEs.

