# **7 DISCONTINUATION OF STUDY INTERVENTION AND PARTICIPANT WITHDRAWAL**

## **7.1 Discontinuation of Study Intervention**

Discontinuation of study intervention does not represent withdrawal from the study.

As certain data on clinical events beyond study intervention discontinuation may be important to the study, they must be collected through the participant's last scheduled follow-up, even if the participant has discontinued study intervention. Therefore, all participants who discontinue study intervention prior to completion of the protocol-specified treatment regimen will still continue to participate in the study as specified in Section 1.3 and Section 8.1.9, or if available, a protocol clarification letter.

Participants may discontinue study intervention at any time for any reason or be discontinued from the study intervention at the discretion of the investigator should any untoward effect occur. In addition, a participant may be discontinued from study intervention by the investigator or the Sponsor if study intervention is inappropriate, the study plan is violated, or for administrative and/or other safety reasons. Specific details regarding procedures to be performed at study intervention discontinuation are provided in Sections 8.1.9.

A participant must be discontinued from study intervention but continue to be monitored in the study for any of the following reasons:

- The participant or participant's legally acceptable representative requests to discontinue study intervention.
- The participant's treatment assignment has been unblinded by the investigator, or through the emergency unblinding call center.
- The participant has a medical condition or personal circumstance which, in the opinion of the investigator and/or Sponsor, placed the participant at unnecessary risk from continued administration of study intervention.
- The participant has a confirmed positive serum pregnancy test.

For participants who are discontinued from study intervention all applicable discontinuation activities will be performed according to Section 8.1.9, or if available, a protocol clarification letter.

Discontinuation from study intervention is "permanent." Once a participant is discontinued from study intervention, they shall not be allowed to restart study intervention.

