### **8.1.10     Participant Blinding/Unblinding**

**STUDY INTERVENTION IDENTIFICATION INFORMATION IS TO BE UNMASKED ONLY IF NECESSARY FOR THE WELFARE OF THE PARTICIPANT. EVERY EFFORT SHOULD BE MADE NOT TO UNBLIND.**

For emergency situations where the investigator or medically qualified designee (consistent with local requirements) needs to identify the intervention used by a participant and/or the dosage administered, he/she will contact the emergency unblinding call center by telephone and make a request for emergency unblinding. As requested by the investigator or medically qualified designee, the emergency unblinding call center will provide the information to him/her promptly and report unblinding to the Sponsor. Prior to contacting the emergency unblinding call center to request unblinding of a participant's intervention assignment, the investigator who is qualified physician should make reasonable attempts to enter the intensity of the AEs observed, the relation to study drug, the reason thereof, etc., in the medical chart. If it is not possible to record this assessment in the chart prior to the unblinding, the unblinding should not be delayed.

In the event that unblinding has occurred, the circumstances around the unblinding (eg, date, reason, and person performing the unblinding) must be documented promptly, and the Sponsor Clinical Director notified as soon as possible.

Once an emergency unblinding has taken place, the investigator, site personnel, and Sponsor personnel may be unblinded so that the appropriate follow-up medical care can be provided to the participant.

Participants whose treatment assignment has been unblinded by the investigator or medically qualified designee and/or nonstudy treating physician must be discontinued from study intervention, but should continue to be monitored in the study.

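### Same-intervention replacement after a broken code lets the site infer the replacement's arm; Section 5.5 needs an exception for disclosed allocations

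*Combined protocol and SAP*

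**What the plan says.** Four sets of rules meet here.

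- **Stopping treatment.** Section 7.1 introduces its mandatory list with "A participant must be discontinued from study intervention but continue to be monitored in the study for any of the following reasons", and one entry is "The participant's treatment assignment has been unblinded by the investigator, or through the emergency unblinding call center". Section 8.1.10 agrees: such participants "must be discontinued from study intervention, but should continue to be monitored in the study".
- **Who may learn the code.** Section 8.1.10: "Once an emergency unblinding has taken place, the investigator, site personnel, and Sponsor personnel may be unblinded", for the purpose of follow-up care.
- **Replacement.** Section 5.5: "If a participant discontinues from study intervention or withdraws from the study, a replacement participant may be enrolled". It continues: "The replacement participant will generally receive the same intervention or intervention sequence (as appropriate) as the participant being replaced". The replacement gets a new number, which the site obtains from the Sponsor. Section 6 also requires contact with the Sponsor before that person is dosed.
- **Blinding and its purpose.** Section 6.3.3 keeps the participant, the investigator and the Sponsor staff involved in dosing or evaluation unaware of the arm. Section 4.2.2 gives the reason for placebo: "A matched placebo-control will be included to reduce bias with regards to the participant reporting and investigator assessment of AEs".

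**The concern.** Each rule is ordinary by itself. Read in order, they let a disclosed allocation carry over to a new participant. The site knows who the replacement is, because it asked for the number. It also holds the protocol that says the arm will generally match. A new randomization number does not restore the blind when the arm is tied to someone whose arm is known.

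Safety and tolerability are the primary objective. The investigator grades the intensity and causality of adverse events (10.3.4), the investigator or a designee completes the BARS, AIMS and SAS (8.3.6), and the investigator shares titration and cohort decisions with the Sponsor (6.6, 4.1). For the replacement, those judgements could be made with the arm inferred. The Synopsis lists no data monitoring committee, so no planned independent body would offset this.

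**Working it through.** No sample-size or precision figure in the plan depends on the replacement rule, so the main check is of the chain itself. The arithmetic sizes the effect and the cost of the fix.

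**1. The chain**
- Code broken: treatment must stop (7.1, 8.1.10).
- Code broken: site and Sponsor staff may know the arm (8.1.10).
- Treatment stopped for any reason: replacement is allowed, generally on the same arm (5.5).
- The site requests the replacement's number (5.5), so it can identify that person.
- Sections 5.5, 6, 6.3.3, 6.8, 7.1, 8.1.7, 8.1.9 and 8.1.10 contain no bar on replacement after a code break, no fresh draw, and no requirement for another site or assessor.

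**2. What the site could guess otherwise**

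Table 2 allocates 12 active and 4 placebo in Panels D and E, and 10 active and 2 placebo in Panels F and G. Guessing active for everyone is right with probability 12/16 = 75%, or 10/12 = 83%. For a same-arm replacement of a disclosed participant it approaches certainty in either arm. The word *generally* in 5.5 is what keeps it short of certainty.

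**3. Share of the data**

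Section 9.5 puts everyone with at least one dose in the safety population, so a dosed predecessor is still counted. With initial size *n*, the replacement is 1/(*n* + 1) of those treated. Initial sizes come from Section 4.1: 8 in Panel D, 4 in Panel E, 6 in Panel F. For Panel G, 4 is inferred because it is run like Panel E.
- *n* = 4: 1/5 = 20%
- *n* = 6: 1/7 = 14%
- *n* = 8: 1/9 = 11%

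These shares apply only if the replacement's data are in hand before the cohort decision, which the documents do not require. In a full panel the share is 1/17 = 6% (D, E) or 1/13 = 8% (F, G).

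For a placebo replacement in a full panel or regimen:
- Panels F and G: 1/(2 + 1) = 1/3 of treated placebo participants
- Panels D and E: 1/(4 + 1) = 1/5

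**4. PK cost of a fresh draw**

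The Table 4 AUC0-24hr half-widths follow from t(0.95, n1 + n2 − 2) × SD × √(1/n1 + 1/n2).
- Schizophrenia, SD 0.38, 12 vs 12: 1.717 × 0.38 × 0.408 = 0.266, as stated in Table 4.
- Healthy, SD 0.60, 10 vs 12: 1.725 × 0.60 × 0.428 = 0.443, as stated in Table 4.

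With one fewer active elderly participant:
- 11 vs 12: 1.721 × 0.38 × 0.417 = 0.273
- 9 vs 12: 1.729 × 0.60 × 0.441 = 0.457

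A draw at the panel's ratio replaces an active participant with placebo with probability 4/16 = 25% (D, E) or 2/12 = 17% (F, G).

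**The case against.** The strongest reply is that every link is conditional. Codes are broken only in emergencies (6.8, 8.1.10). Under 5.5, "a replacement participant may be enrolled if deemed appropriate by the investigator and Sponsor", and the arm is only *generally* the same. The Sponsor issues the number and is contacted before dosing, so it could already decline to replace or assign another arm. The code may reach only a treating physician outside the study. This is a multi-site trial, and 5.5 does not say the replacement must come from the same site. All of this stands. It makes the case rare and the arm inferable rather than known. It does not close the gap, because the default in 5.5 is the same arm and nothing tells the Sponsor to depart from it after disclosure.

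A reader might go further in four ways that the documents do not support.

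- *One replacement is 12.5% to 25% of a decision cohort, or half the placebo group in Panels F and G.* That drops the dosed predecessor, who stays in the safety population. The 2 placebo participants also belong to the full allocation of 12; the documents do not give the placebo count within an initial cohort.
- *The replacement is not randomised, which is a further defect.* That is true of every same-arm replacement, and it sits awkwardly with 8.1.7, but it is not specific to a broken code.
- *The predecessor must have had a serious event.* Section 8.1.10 requires only that unmasking be needed for the participant's welfare.
- *All reporting is unblinded.* Nothing in the chain reveals the arm to the replacement participant, so self-report keeps its blind.

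**Conclusion.** The gap is real but narrow. The replacement rule works against the blinding in 6.3.3 and the purpose of placebo in 4.2.2, and no safeguard appears elsewhere. It affects investigator assessment of adverse events, EPS ratings and tolerability decisions for a replacement whose predecessor's code became known at that site. Plasma PK is little affected. Part 1 is clinically complete according to the Synopsis, so only Part 2 remains exposed. There are no hypotheses and safety is summarised descriptively, so no error rate is at stake.

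The sizes in the working assume that the predecessor was dosed, the replacement is enrolled at the same site on the same arm, and, for the cohort shares, its data reach the decision. The documents give no rate of code breaks, so no expected frequency can be stated. The change is worth making because it is cheap and because decisions in Part 2 rest on very few participants.

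**What to change.** Add an exception to Section 5.5, for example: *If the replaced participant's assignment has been disclosed to the investigator, site staff or blinded Sponsor staff, any replacement at that site is assigned by a fresh blinded random draw from a reserve replacement list with the panel's allocation ratio, and is identified in the CSR.* Keep same-intervention replacement where the code is unbroken.

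A reserve list is better than the next unused number on the main schedule. That number would use up a planned slot, or might not exist once a panel is fully allocated.

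The cost is one sentence, a reserve list for each remaining panel, and an instruction to the allocation group and the unblinded pharmacist. The split may be off by one. Losing one active participant widens the AUC0-24hr log half-width from 0.266 to about 0.273 (schizophrenia) or from 0.443 to about 0.457 (healthy). Alternatively, a placebo participant may be replaced by an active one, with probability 12/16 = 75% in Panels D and E or 10/12 = 83% in F and G. In F or G that leaves one placebo participant on treatment instead of two. No safety data are lost, because the unblinded participant stays in the safety population and under monitoring.

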## **6 STUDY INTERVENTION**

Study intervention is defined as any investigational intervention(s), marketed product(s), placebo, or medical device(s) intended to be administered to a study participant according to the study protocol.

Clinical supplies, study intervention(s) provided by the Sponsor, will be packaged to support enrollment and replacement participants as required. When a replacement participant is required, the Sponsor or designee needs to be contacted prior to dosing the replacement participant. Clinical supplies will be affixed with a clinical label in accordance with regulatory requirements.

## 6.1 Study Intervention(s) Administered

The study intervention(s) to be used in this study are outlined in [Table 1].

Table 1 Study Interventions

Arm Name	Arm Type	Intervention Name	Intervention Type	Dose Formulation	Unit Dose Strength(s)	Dosage Level(s)	Route of Administration	Regimen	Use	IMP/NIMP	Sourcing
Active	Experimental	MK-8189	Drug	Tablet	4 mg 12 mg	All dose levels	Oral	Titration Regimens 1, 2, 3 and Panel D/F dose regimen	Experimental	IMP	Provided Centrally
Placebo	Placebo Comparator	MK-8189	Drug	Tablet	0 mg	All dose levels	Oral	Titration Regimens 1, 2, 3 and Panel D/F dose regimen	Placebo	IMP	Provided Centrally

The classification of Investigational Medicinal Product (IMP) and Non-Investigational Medicinal Product (NIMP) in this table is based on guidance issued by the European Commission and applies to countries in the European Economic Area (EEA). Country differences with respect to the definition/classification of IMP/NIMP may exist. In these circumstances, local legislation is followed.

All supplies indicated in [Table 1] will be provided per the "Sourcing" column depending upon local country operational requirements. If local sourcing, every attempt should be made to source these supplies from a single lot/batch number.

Refer to Section 8.1.8 for details regarding administration of the study intervention.

All placebos were created by the Sponsor to match the active product.

## **6.2 Preparation/Handling/Storage/Accountability**

### **6.2.1 Dose Preparation**

There are no specific calculations or evaluations required to be performed in order to administer the proper dose to each participant. The rationale for selection of doses to be used in this study is provided in Section 4.3.

### **6.2.2 Handling, Storage, and Accountability**

The investigator or designee must confirm appropriate temperature conditions have been maintained during transit for all study intervention received, and any discrepancies are reported and resolved before use of the study intervention.

Only participants enrolled in the study may receive study intervention, and only authorized site staff may supply or administer study intervention. All study interventions must be stored in a secure, environmentally controlled, and monitored (manual or automated) area in accordance with the labeled storage conditions with access limited to the investigator and authorized site staff.

The investigator, institution, or the head of the medical institution (where applicable) is responsible for study intervention accountability, reconciliation, and record maintenance (ie, receipt, reconciliation, and final disposition records).

For all study sites, the local country Sponsor personnel or designee will provide appropriate documentation that must be completed for drug accountability and return, or local discard and destruction if appropriate. Where local discard and destruction is appropriate, the investigator is responsible for ensuring that a local discard/destruction procedure is documented.

The study site is responsible for recording the lot number, manufacturer, and expiry date for any locally purchased product (if applicable) as per local guidelines unless otherwise instructed by the Sponsor.

The investigator shall take responsibility for and shall take all steps to maintain appropriate records and ensure appropriate supply, storage, handling, distribution, and usage of study interventions in accordance with the protocol and any applicable laws and regulations.

## 6.3 Measures to Minimize Bias: Randomization and Blinding

### 6.3.1 Intervention Assignment

Participants will be assigned randomly according to a computer-generated allocation schedule.

The sample allocation schedule for Parts 1 and 2 is provided in [Table 2].

Table 2 Sample Allocation Schedule

Part 1							
Panel	Patients (n)	Day 1	Day 2	Day 3	Days 4-7		
A	12	16 mg QD			24 mg QD		
	4	PBO			PBO		
B	12	24 mg					
	4	PBO					
C	12	8 mg QD	16 mg QD	24 mg QD			
	4	PBO	PBO	PBO			
Part 2							
Panel	Patients (n)	Days 1-3	Days 4-6	Days 7-13			
D/F	12 (Panel D); 10 (Panel F)	8 mg QD	16 mg QD	24 mg QD			
	4 (Panel D); 2 (Panel F)	PBO	PBO	PBO			
Part 2							
Panel	Patients (n)	Days 1-3	Days 4-10				
E/G TR1	12 (Panel E); 10 (Panel G)	16 mg QD	24 mg QD				
	4 (Panel E); 2 (Panel G)	PBO	PBO				
Part 2							
Panel	Patients (n)	Days 1-7					
E/G TR 2	12 (Panel E); 10 (Panel G)	24 mg QD					
	4 (Panel E); 2 (Panel G)	PBO					
Part 2							
Panel	Patients (n)	Day 1	Day 2	Days 3-9			
E/G TR 3	12 (Panel E); 10 (Panel G)	8 mg QD	16 mg QD	24 mg QD			
	4 (Panel E) 2 (Panel G)	PBO	PBO	PBO			

TR = Titration Regimen; n=number; PBO=placebo; QD=once daily

### **6.3.2 Stratification**

No stratification based on age, sex, or other characteristics will be used in this study.

### **6.3.3 Blinding**

A double-blinding technique will be used. MK-8189 and placebo will be prepared and/or dispensed in a blinded fashion by an unblinded pharmacist or qualified study site personnel. The participant, the investigator, and Sponsor personnel or delegate(s) who are involved in the study intervention administration or clinical evaluation of the participants are unaware of the intervention assignments.

### **6.4 Study Intervention Compliance**

Interruptions from the protocol-specified treatment plan require consultation between the investigator and the Sponsor and written documentation of the collaborative decision on participant management.

When the individual dose for a participant is prepared from a bulk supply, the preparation of the dose will be confirmed by a second member of the study site staff.

When participants are dosed at the site, they will receive study intervention directly from the investigator or designee, under medical supervision. The date and time of each dose administered in the clinic will be recorded in the source documents and recorded in the CRF. The dose of study intervention and study participant identification will be confirmed at the time of dosing by a member of the study site staff other than the person administering the study intervention. Study site personnel will examine each participant's mouth to ensure that the study intervention was ingested.

### **6.5 Concomitant Therapy**

Concurrent use of any prescription or nonprescription medication, during the ongoing study (ie, after randomization or intervention allocation) must first be discussed between the investigator and Sponsor prior to administration, unless appropriate medical care necessitates that therapy or vaccination should begin before the investigator and Sponsor can consult. The participant will be allowed to continue in the study if both the Sponsor and the investigator agree.

Acetaminophen and antacids (eg, magnesium hydroxide) may be used for minor ailments without prior consultation with the Sponsor.

Medications to treat mild chronic conditions such as hypothyroidism, diabetes, high blood pressure, chronic respiratory conditions or other mild medical conditions are allowed during the study if the prescribed dose and regimen of medication is stable for at least three months prior to screening and there are no expected changes in co-medication during the study. Moderate to strong inhibitors or inducers of CYP3A and/or CYP2C9 are not allowed as MK-8189 is being metabolized by these CYP enzymes and co-administration of inhibitors or

inducers may potentially alter the metabolism and PK of MK-8189. In addition, MK-8189 is a mild inducer of CYP2B6 in human hepatocytes at drug concentrations of  $\geq 10 \mu\text{M}$  and therefore co-medication with substrates for CYP2B6 should be avoided (ie, efavirenz and bupropion). See also Section 6.5.1 on rescue medication.

### 6.5.1     Rescue Medications and Supportive Care

For the treatment of EPS, such as **acute dystonia**, all participants may be treated with an anticholinergic. If the symptoms are unresponsive to anticholinergic treatment, a benzodiazepine can be used.

In case the participant presents with signs of **akathisia** without signs of dystonia, the participant can be treated with a  $\beta$ -adrenergic blocker. If symptoms do not disappear with the  $\beta$ -adrenergic blocker, treatment with an anticholinergic may be used. An anticholinergic may be used as first-line treatment in the case that a  $\beta$ -adrenergic blocker is not a preferred treatment based on a participant's medical history and/or concomitant medication.

Anticholinergics, benzodiazepines and  $\beta$ -adrenergic blockers are often used in the treatment of EPS and are considered standard practice. Oral anticholinergic treatment is also used as concomitant medication to prevent EPS symptoms with antipsychotic medication.

Patients will be washed off from their antipsychotic treatment (Section 8.1.5.1). During the washout and treatment period, a benzodiazepine and zolpidem may be used to treat withdrawal symptoms. The drugs indicated above should not be inhibitors or inducers of CYP3A and CYP2C9 (see Section 6.5 for further details), thus no effect on the PK of MK-8189 would be expected during coadministration.

### 6.6     Dose Modification (Escalation/Titration/Other)

In Part 1, Panel A (Titration Regimen 1), Panel C (Titration Regimen 3), and if applicable for Part 2 (ie, a treatment with a titration scheme is selected), dose titration decisions will be made jointly by the investigator and the Sponsor. However, if a participant needs to be discontinued or have a dose reduction based on safety/tolerability, the principal investigator may do so independent of consultation with the Sponsor.

For Titration Regimen 1 and the dose regimen given in Panel D and Panel F, each dose titration decision for each individual participant will occur after 3 days of dosing per dose level. For Titration Regimen 3, the titration decision for each individual will be made following the 16 mg Dose (Day 2).

For Titration Regimen 2 (no titration), safety and tolerability data will be reviewed following 3 Days of dosing to determine if dosing for an individual participant should continue at that dose level.

Dose titration decisions for each participant will be based on available (as per the SoA) safety variables: VS, 12-lead safety ECG, laboratory safety tests, AEs, C-SSRS, BPRS, and EPS evaluations from the previous dose levels.

If, as judged by the Sponsor and investigator, the safety and tolerability data do not justify dose titration, the dose will not be increased as planned. Instead, participants may:

- Skip a single dose and dosing may continue at the same dose level or adjusted downwards
- Receive the same dose level to further explore safety and tolerability at that level
- Receive a lower dose of the study intervention
- Stop dosing

If appropriate medical care necessitates dosing to be stopped or a lower dose given, the investigator may do so without consultation with the Sponsor.

Participant discontinuation criteria are outlined in Section 7.

